4.3 Analysis Data Sets

The following analysis sets will be used in the study:

Safety Analysis Set: All subjects who receive at least one dose of any study medication (even a partial dose), grouped by actual treatment received. This set will serve as the basis for the evaluation of all safety data, as well as demographic and baseline disease characteristics, prior cancer therapy, study drug exposure, and dose modifications. Unless noted otherwise, safety data will be summarized or listed separately for Part 1 and Part 2.

Intent to Treat (ITT) Analysis Set: All subjects randomized in Part 2 of the study, as assigned to treatment. The ITT population is the primary population for the analysis of Overall Survival (OS) and will also be used to evaluate all secondary efficacy endpoints and subject characteristics.

Modified Intent to Treat (mITT) Analysis Set: All subjects who were randomized and received at least one dose of the study drug in Part 2 of the study, as assigned to treatment. The mITT population is the primary population for the sensitivity analysis of Overall Survival (OS) and all secondary efficacy endpoints.

Efficacy Evaluable: All subjects randomized in Part 2 of the study who have measurable disease at baseline, receive any amount of the assigned study treatment, and have at least one evaluable post-baseline tumor assessment. Subjects with measurable disease must have at least one measurable lesion. Measurable lesions are defined (according to RECIST) as those that can be accurately measured in at least one dimension (longest diameter to be recorded) as ≥ 20

mm by chest x-ray, as ≥ 10 mm with CT scan, or ≥ 10 mm with calipers by clinical exam. Together with the ITT population, the Efficacy Evaluable group will be used to evaluate ORR and other tumor response endpoints.

Per Protocol Population: All subjects randomized in Part 2 of the study who satisfy the following criteria:

- 1) Completed at least 2 cycles of the assigned treatment
- 2) Qualified for the study based on SCLC diagnosis and prior therapies (i.e., met protocol inclusion criteria 3.1.3, 3.1.4, 3.1.5; did not meet exclusion criterion 3.2.2)
- 3) Received at least 80% of the prescribed study drug (i.e., their average dose during the treatment period was at least 80% of the planned dose).

This population will be used for sensitivity analysis of the primary efficacy endpoint.

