4.9.2 Progression-Free Survival (PFS)

PFS is defined as the time from the date of randomization to the date of first documentation of tumor progression or death from any cause, whichever occurs first. Tumor response assessments will be performed using Response Evaluation Criteria In Solid Tumors (RECIST) version 1.1.

PFS will be evaluated using the stratified log-rank test, as described for OS, with specific conventions for censoring. PFS data will be censored on the date of the last tumor assessment documenting absence of PD for subjects who 1) are given anti-tumor treatment other than the study treatment prior to observing objective tumor progression; 2) are removed from the study prior to documentation of objective tumor progression; 3) are ongoing and do not have objective tumor progression at the time of the analysis. Death or disease progression that occurs after more than one missed visit (i.e., 12 weeks) will be censored on the date of the last tumor assessment prior to the first missed visit. Subjects with no post-baseline tumor assessments will be censored on the date of randomization.

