4.9.3 Overall Response Rate (ORR)

ORR is the percentage of subjects with best overall response (BOR) of either CR or PR. Subjects with no post-baseline results will be considered non-responders. ORR will be calculated by treatment group for ITT and Efficacy Evaluable subjects. Both confirmed and unconfirmed CR/PR will be tabulated. The rates will be presented along with two-sided 95% exact confidence intervals. The 95% CIs will be derived using the Clopper-Pearson method. This method is commonly used in the literature for reporting tumor response rates and is conservative, providing no less than 95% coverage probability even for small N.

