4.9.4 Clinical Benefit Rate (CBR)

The CBR is the percentage of subjects with either a CR or PR, or SD. The rates and the exact 95% CIs will be provided for each treatment group. Subjects with no post-baseline tumor assessments will be considered to have achieved no clinical benefit. Subjects will be classified as having stable disease if assessed as SD (or better) at least 6 weeks after first dose date.

Binary endpoints (ORR and CBR) will be analyzed using stratified Cochran-Mantel-Haenszel chi-square tests, with two-tailed $\alpha=0.05$. Odds ratios will be presented along with corresponding 95% confidence intervals.

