4.9.5 Other Efficacy Outcomes

Treatment groups will also be compared on the basis of the following additional efficacy outcomes, with tumor response defined by RECIST criteria (version 1.1):

Best Overall Response (BOR)

The BOR is the best response observed from the start of study treatment until the last assessment of tumor response recorded during follow-up or the start of any post treatment cancer therapy (whichever is sooner), taking into account any requirement for confirmation (i.e., at least 4 weeks apart). The number and percentage of subjects in each BOR category (i.e., CR, PR, SD, PD, and unevaluable) will be summarized by treatment group. Subjects with unconfirmed CR or PR assessments will be categorized separately. The table will include a category for subjects who died or discontinued the study due to disease progression prior to the first tumor assessment, as well as ongoing subjects without a tumor assessment prior to the data cut-off date for analysis. Subjects will be classified as having stable disease if assessed as SD (or better) at least 6 weeks after first dose date.

Data listings will display target lesion measurements and non-target lesion response assessments at each timepoint, together with the level of tumor response assigned by the investigator.

Time to Response (TTR)

The TTR is defined as the time interval between the date of randomization and the date of first documented CR or PR. CR or PR requires confirmation at least 4 weeks apart. Once it is confirmed, the first documented CR or PR will be considered as the start of the response. TTR will be descriptively summarized for subjects who responded.

Duration of response (DOR)

The DOR is defined as the time interval between the date of first documented PR or CR and the subsequent first date of disease progression as determined by radiological assessment using RECIST criteria (version 1.1) or death.

Subjects who do not experience disease progression and have not died will be censored on the date of their last tumor assessment. Disease progression that occurs after more than one missed visit (i.e., 12 weeks) will be censored on the date of the last tumor assessment prior to the first

missed visit. For OS, the death date will be used as an event time, no matter how many prior visits were missed.

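### As written, a subject who dies before the first scan is censored out of PFS at randomization, although death is a PFS event

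*SAP*

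**What the plan says.** SAP 4.9.2 measures PFS from randomization "to the date of first documentation of tumor progression or death from any cause, whichever occurs first". Among its censoring conventions is this sentence: "Subjects with no post-baseline tumor assessments will be censored on the date of randomization". Protocol 10.9.2 has the same definition and the same rule. Neither makes an exception for a subject who has died.

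The only convention that mentions death concerns missed visits: "Death or disease progression that occurs after more than one missed visit (i.e., 12 weeks) will be censored". Scans are due every 6 weeks from randomization, within 7 days either way (protocol 8.3), so a death before week 6 has missed no visit.

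The other tested endpoints treat the same subjects as follows in the ITT set:

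- **OS:** the death is an event. SAP 4.9.5 adds: "For OS, the death date will be used as an event time, no matter how many prior visits were missed". That sentence is confined to OS.
- **ORR (SAP 4.9.3):** "Subjects with no post-baseline results will be considered non-responders".
- **CBR (SAP 4.9.4):** "Subjects with no post-baseline tumor assessments will be considered to have achieved no clinical benefit".

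The plan expects such subjects, since for best overall response SAP 4.9.5 says: "The table will include a category for subjects who died or discontinued the study due to disease progression prior to the first tumor assessment". The Efficacy Evaluable set also leaves them out, because its members must "receive any amount of the assigned study treatment, and have at least one evaluable post-baseline tumor assessment". That set supplements the ITT analyses of response.

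**The concern.** A subject censored at time zero is in no log-rank risk set and in effect leaves the comparison. Read literally, the rule removes from PFS every subject who dies unscanned, including those who fail fastest. The PFS curve then cannot show a death before the first scan, and an early-death imbalance in either direction disappears from the comparison.

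PFS is the first secondary endpoint after OS in the alpha-controlled sequence (SAP 4.9), and protocol 10.1 links the secondary endpoints to possible labeling claims. SAP 8.1 lists two PFS summaries, ITT and mITT, and no alternative censoring rule is given for either. If the sentence was meant only for subjects who are alive without a scan, it does not say so, and two programmers could build different PFS datasets from it.

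**Working it through.** **Inputs from the documents.** 184 subjects each in Groups A and B; OS medians 6 and 8.3 months; HR 0.725; 306 deaths; two-sided alpha 0.05; uniform entry over 10 months plus 14 months of follow-up (SAP 4.2). First scan at week 6 ± 1 week (protocol 8.3). Months = days / 30.42 (SAP 7.2.1).

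**The plan's own figures reproduce.**

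- Power = Φ(√(306/4) × |ln 0.725| − 1.96) = Φ(8.746 × 0.3216 − 1.96) = Φ(0.853) = 80.3%, against the stated 80%.
- Expected deaths at month 24 per group = 184 × [1 − (e^(−14λ) − e^(−24λ)) / (10λ)], with λ = ln 2 / median. This gives 162.4 + 145.3 = 307.6, against 306.

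**Deaths before the first scan.** Take t = 42/30.42 = 1.381 months, and let f be the early hazard as a fraction of the constant hazard.

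- Group A: 184 × (1 − e^(−ln 2 × t × f / 6)) = 27.1 at f = 1.
- Group B: 184 × (1 − e^(−0.725 × ln 2 × t × f / 6)) = 20.1 at f = 1.
- Total: 47.2 of 368 (12.8%), or 40 to 54 for a first scan at week 5 to 7. It is 24.4 at f = 0.5 and 12.4 at f = 0.25.

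An end-of-treatment scan before death lowers the count. A death after a missed week-6 scan raises it.

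**Effect on the PFS test.** Simulation with 4,000 trials per scenario, cut at the 306th death in A and B. Group A median OS is held at 6 months, with hazard multiplied by f in the first 6 weeks. The Group B hazard is 0.725 times that of Group A throughout. Progression is independent and exponential, seen at the next 6-weekly scan. The log-rank test is unstratified, because the stratum mix is not given. Median time to progression (TTP), the progression HRs, f and the imbalance below are assumptions; the documents give none of them.

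TTP 3.5 months, first scan at week 6. Cells show definition vs literal rule:

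| Progression HR | f | PFS power | OS and PFS both significant |
|---|---|---|---|
| 0.725 | 1 | 85.3% vs 79.7% | 71.8% vs 67.3% |
| 0.725 | 0.5 | 85.6% vs 83.0% | 71.7% vs 69.6% |
| 0.725 | 0.25 | 86.2% vs 84.7% | 71.8% vs 70.5% |
| 0.80 | 1 | 69.8% vs 61.1% | 60.6% vs 52.6% |
| 0.80 | 0.5 | 71.0% vs 65.7% | 61.7% vs 56.8% |
| 0.80 | 0.25 | 70.4% vs 67.8% | 60.3% vs 57.9% |

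The range was widened to TTP 2.5 to 4.5 months, f from 0.25 to 1, and first scan at week 5 to 7 (varied at f = 1 only). The loss in PFS power is then 1.4 to 7.1 points (HR 0.725) or 2.5 to 12.6 points (HR 0.80). The loss in the chance that both tests succeed is 1.3 to 6.4 or 2.0 to 11.8 points. The Monte Carlo standard error of a loss is at most 0.6 points. OS power stays at 78.8% to 81.5%. The largest shift in the PFS HR is 0.794 vs 0.808. At TTP 3.5, Group A 3-month PFS reads 0.481 under the rule instead of 0.410 at f = 1, and 0.461 instead of 0.443 at f = 0.25.

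**Early imbalance.** Assume 10% vs 5% dead by week 6 (about 18 vs 9 subjects), the plan's OS hazards afterwards, and TTP 3.5. Cells show definition vs rule:

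| Excess in | Progression HR | PFS HR | PFS power | Both significant |
|---|---|---|---|---|
| Group B | 0.725 | 0.80 vs 0.74 | 61.1% vs 83.7% | 37.7% vs 46.2% |
| Group B | 0.80 | 0.85 vs 0.79 | 39.7% vs 65.3% | 28.2% vs 40.0% |
| Group A | 0.725 | 0.72 vs 0.74 | 91.3% vs 82.6% | 81.8% vs 74.6% |
| Group A | 0.80 | 0.76 vs 0.79 | 80.2% vs 65.7% | 73.4% vs 60.8% |

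**The case against.** The strongest reply is that censoring conventions always depart from the bare definition, and SAP 4.9.2 announces that it uses them. The other conventions censor at the last tumor assessment, and in the SAP the no-scan sentence comes after them. It can therefore be read as supplying a date when no assessment exists, for subjects who are being censored anyway. That is a sensible intention, but neither document states it, and the sentence covers all subjects without a scan. The reading needs the same edit.

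Other points have some force:

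- SAP 7.2 says that some table-specific rules sit in the mock-ups, which are not in the documents. They might narrow the rule. The text of the plan does not.
- The count of 47 lies toward the top of its range. Eligibility requires a life expectancy of at least 12 weeks and ECOG 0 or 1, and the end-of-treatment visit includes a scan unless progression is already documented. The lower-hazard rows (24 and 12 deaths) allow for fewer early deaths.
- Because OS gates PFS, the joint probabilities are the relevant ones for a claim. They move less than ungated PFS power when the excess is in Group B: 8.5 and 11.8 points rather than 22.6 and 25.6.
- When early deaths follow the OS hazard ratio, the PFS HR barely moves. Material bias in the estimate needs an imbalance, and the one shown is assumed.

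**Conclusion.** The concern holds. The no-scan sentence contradicts the PFS definition for a subject who dies before the first scan, and by implication the missed-visit rule, which censors a death only after more than one missed visit. This conclusion rests on the text and on none of the assumed figures.

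The size is uncertain. Between about 12 and 54 of 368 subjects would lose their event over the early hazards and scan weeks examined, provided that no scan precedes death. This range is illustrative and is not a bound. The cost runs from negligible to moderate power loss when early deaths follow the OS hazard ratio. With an imbalance, the rule can favor or penalize Group B.

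The primary OS test is untouched, and the confirmatory consequence is limited to the PFS test when OS is significant. Early deaths also remain visible in OS, in the best-overall-response category and in Listing 16.2.6.1. The sentence should be corrected, but it does not threaten the trial's main conclusion.

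**What to change.** Before unblinding, replace the no-scan sentence in SAP 4.9.2 with, for example:

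*A subject without any post-baseline tumor assessment who dies within 12 weeks of randomization is a PFS event on the date of death, provided that no other anti-tumor treatment was started and the subject was not removed from the study before death. Every other subject without a post-baseline tumor assessment is censored on the date of randomization.*

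This keeps the precedence of the first two PFS censoring rules and the 12-week limit that the SAP already attaches to more than one missed visit. Stating the limit in weeks also avoids a dispute over the 7-day scan window. Merely adding that the subject has not died would be shorter. But a late unscanned death would then fall under the missed-visit rule, whose censoring date would be the baseline scan, up to 28 days before randomization (protocol 8.1).

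A PFS sensitivity analysis that counts all deaths as events is optional.

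The cost is one sentence in the SAP. The SAP supersedes the protocol on statistical matters (SAP 1), so the SAP edit is enough, with the difference from protocol 10.9.2 noted there. The protocol sentence can be aligned at the next amendment. No new data are needed: death dates, study discontinuation and post-study cancer therapy are already collected and listed.

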4.9.3 Overall Response Rate (ORR)

ORR is the percentage of subjects with best overall response (BOR) of either CR or PR. Subjects with no post-baseline results will be considered non-responders. ORR will be calculated by treatment group for ITT and Efficacy Evaluable subjects. Both confirmed and unconfirmed CR/PR will be tabulated. The rates will be presented along with two-sided 95% exact confidence intervals. The 95% CIs will be derived using the Clopper-Pearson method. This method is commonly used in the literature for reporting tumor response rates and is conservative, providing no less than 95% coverage probability even for small N.

4.9.4 Clinical Benefit Rate (CBR)

The CBR is the percentage of subjects with either a CR or PR, or SD. The rates and the exact 95% CIs will be provided for each treatment group. Subjects with no post-baseline tumor assessments will be considered to have achieved no clinical benefit. Subjects will be classified as having stable disease if assessed as SD (or better) at least 6 weeks after first dose date.

Binary endpoints (ORR and CBR) will be analyzed using stratified Cochran-Mantel-Haenszel chi-square tests, with two-tailed $\alpha=0.05$. Odds ratios will be presented along with corresponding 95% confidence intervals.

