4. ENROLLMENT AND RANDOMIZATION PROCEDURES

Eligible and consented subjects will be enrolled in the study. In Part 1, each subject will receive dinutuximab in combination with irinotecan and will start treatment within 3 working days of enrollment. Subjects participating in Part 2 of the study will be randomized in an open-label fashion using a 2:2:1 ratio to one of three treatment groups and will begin treatment within 3 working days of randomization. Randomization will be performed using a web-based randomization and product inventory control (RPIC) system provided by a third-party vendor. Specific procedures for randomization through RPIC are contained in the study procedures manual.

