The time points for post dose samples start from the end of the infusion (e.g., 24 hours post dose = 24 hours after infusion end). Serial PK blood draws will be repeated with the first dose change (reduction or escalation). A validated assay will be used to measure concentration of dinutuximab. Details regarding sampling time points and procedures can be found in the lab manual.

- Sparse blood samples for population PK analysis during Cycle 1 at 2 time points and during Cycle 3 at 6 time points (**Part 2 Group B only**):

| Time points | Cycle 1 | |
|-------------|--|--|
| | Pre-dose | Infusion end |
| Windows | Anytime prior to dosing on the day of dosing | Up to 10 minutes after the end of the infusion |

| Time points | Cycle 3 | | Post dose, hours (Day) | | | |
|-------------|--|--|------------------------|--------------|--------------|--|
| | Pre-dose | Infusion end | 24 (Day 2) | 192 (Day 8) | 360 (Day 15) | 528 (Day 22) before the next dose (Cycle 4, Day 1) |
| Windows | Anytime prior to dosing on the day of dosing | Up to 10 minutes after the end of the infusion | ± 30 minutes | ± 60 minutes | | Anytime prior to the next dose on the day of the next dose |

The time points for post dose samples start from the end of the infusion (e.g., 24 hours post dose = 24 hours after infusion end). Details regarding sampling time points and procedures can be found in the lab manual.

- Blood samples for the evaluation of ADA and NAb in plasma pre-dose on Day 1 of all cycles plus Day 8 (+/- 1 day) and Day 15 (+/- 1 day) of Cycle 1 (**Part 1 and Part 2 Group B only**). Details regarding sampling time points and procedures can be found in the lab manual.
- Blood sample for biomarker analysis.
- Blood sample on Day 1 of every cycle to analyze CTC (**Part 2, selected regions only**).
- Disease assessments (CT or MRI of the chest/abdomen with contrast, with careful attention to the liver and adrenal and other locations as clinically indicated) every 6 weeks (+/- 7-day window) from the date of enrollment (Part 1) or randomization (Part 2).*

*Note: For subjects enrolled in Part 2, the timing of disease assessments should not be altered, even in the event of a dose delay or interruption in a cycle. This is very important to prevent or minimize evaluation-time bias.

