8.4. EOT/Safety Visit

The following assessments must be completed within approximately 30 days after the time the Investigator decides to discontinue all study drugs for the subject (dinutuximab and/or chemotherapy) or prior to the initiation of subsequent treatment, whichever occurs first. Any ongoing AEs/SAEs at the time of the EOT/safety visit should be followed as outlined in [Section 9.2](#).

- ECOG performance status.
- Status of ongoing AEs and con meds.
- Hematology (including differential).
- Chemistry (BUN, creatinine, glucose, uric acid, bicarbonate, calcium, chloride, phosphorus, potassium, sodium, LDH, albumin, total protein, magnesium, ALP, AST, ALT, total bilirubin).

- Blood samples for post-treatment immunogenicity (**Part 1 and Part 2 Group B only**) **IF** EOT visit occurs within the time frame for the first evaluation (4 weeks [+/- 7 days] of completing dinutuximab) (See [Section 8.5](#)).
- Blood sample for biomarker analysis.
- Blood sample to analyze CTC (**Part 2, selected regions only**).
- Disease assessments (CT or MRI of the chest/abdomen with contrast, with careful attention to the liver and adrenal and other locations as clinically indicated) unless disease progression is previously documented during the study per RECIST.
- Brain MRI (preferred) or brain CT with contrast for subjects with prior evidence of brain metastasis (at baseline) unless disease progression is previously documented during the study per RECIST.
- Recording of planned subsequent anticancer treatment, if any.

Note: All subjects should be followed for overall survival. Subjects enrolled in Part 2 who discontinue treatment prior to the documentation of disease progression should continue to be followed on the disease assessment schedule (every 6 weeks from the date of randomization [+/- 7 days]) until disease progression is documented radiographically per the protocol. At the EOT, further follow-up should be clarified with the subject (for OS, or for disease assessments if applicable) and any such consent for ongoing follow-up must be documented in both the source records and the eCRF. Subject follow-up is critical to prevent or minimize informative censoring for assessment of OS and PFS, the study's primary endpoint and key secondary endpoint, respectively.

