Although a clear progression of “non-target” lesions only is exceptional, the opinion of the treating physician should prevail in such circumstances, and the progression status should be confirmed at a later time by the review panel (or Principal Investigator).

c. Evaluation of New Lesions

The finding of a new lesion should be unequivocal (i.e. not due to difference in scanning technique, imaging modality, or findings thought to represent something other than tumor (for example, some ‘new’ bone lesions may be simply healing or flare of pre-existing lesions). However, a lesion identified on a follow-up scan in an anatomical location that was not scanned at baseline is considered new and will indicate PD. If a new lesion is equivocal (because of small size etc.), follow-up evaluation will clarify if it truly represents new disease and if PD is confirmed, progression should be declared using the date of the initial scan on which the lesion was discovered.

d. Evaluation of Best Overall Response

The best overall response is the best response recorded from the start of the treatment until disease progression/recurrence (taking as reference for progressive disease the smallest measurements recorded since the treatment started). The patient's best response assignment will depend on the achievement of both measurement and confirmation criteria.

For Participants with Measurable Disease (*i.e.*, Target Disease)

| Target Lesions | Non-Target Lesions | New Lesions | Overall Response | Best Overall Response when Confirmation is Required* |
|----------------|--------------------|-------------|------------------|--|
| CR | CR | No | CR | ≥4 wks Confirmation** |

| | | | | |
|--|-----------------------------|-----------|----|---|
| CR | Non-CR/Non-PD | No | PR | ≥4 wks Confirmation** |
| CR | Not evaluated | No | PR | |
| PR | Non-CR/Non-PD/not evaluated | No | PR | |
| SD | Non-CR/Non-PD/not evaluated | No | SD | Documented at least once ≥4 wks from baseline** |
| PD | Any | Yes or No | PD | no prior SD, PR or CR |
| Any | PD*** | Yes or No | PD | |
| Any | Any | Yes | PD | |

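### The SAP counts stable disease only from 6 weeks after first dose, with no window allowance, so SD on an on-schedule first scan is too early on 7 to 12 of the 15 allowed days

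*SAP*

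**What the plan says.** SAP 4.9.4 (CBR) sets the condition: "Subjects will be classified as having stable disease if assessed as SD (or better) at least 6 weeks after first dose date". SAP 4.9.5 repeats it for BOR. Neither section mentions the scan window.

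The scan schedule is in Protocol 8.3. Disease assessments are due "every 6 weeks (+/- 7-day window) from the date of enrollment (Part 1) or randomization (Part 2"). For Part 2 the protocol adds that "the timing of disease assessments should not be altered, even in the event of a dose delay or interruption in a cycle". Under Protocol 4, Part 2 subjects "will begin treatment within 3 working days of randomization".

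Other passages that bear on the point:

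- Protocol 10.9.3 defines CBR as CR, PR or SD and sets no minimum time for SD.
- Protocol 10.9.6 treats as non-responders, for ORR and CBR, subjects who progress, die, drop out or start other anti-tumor therapy before reaching the endpoint.
- Protocol 8.4 calls for an end-of-treatment scan "unless disease progression is previously documented during the study per RECIST".
- Protocol Appendix C, section 5, measures stable disease from the start of treatment. Its BOR table has an SD entry, "Documented at least once ≥4 wks from baseline", footnoted as applying only to non-randomized trials with response as primary endpoint.
- SAP 4.9 places CBR last in the sequence OS, PFS, ORR, CBR. Summary statistics are displayed even if testing stops earlier.

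**The concern.** The SD rule and the scan schedule disagree in two ways. The SD threshold sits on the nominal scan day, so the early part of the permitted window falls short of it. The SD clock also starts at first dose, which can be later than randomization, so part of the remaining window is lost as well.

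Sites cannot correct this by moving scans, because Part 2 scan timing is fixed to randomization. Take two subjects who both show SD on day 44 from randomization and progress at the next scan. The one dosed on the day of randomization is at 44 days and counts as clinical benefit. The one dosed 3 days later is at 41 days and does not. The difference comes from dosing lag, not from the disease. At stake are the CBR estimates and the SD row of BOR.

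**Working it through.** The plan gives no figure of its own to reproduce here. The check is a calendar count.

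**Inputs**

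- SD minimum: 6 weeks = 42 days after first dose (SAP 4.9.4 and 4.9.5).
- First-scan window: day 42 ± 7 from randomization = days 35 to 49, which is 15 days (Protocol 8.3).
- Dosing lag L: up to 3 working days (Protocol 4). For weekday randomization with at most one weekend in between and no holiday (assumption), 3 working days is 3 calendar days from Monday or Tuesday and 5 from Wednesday, Thursday or Friday. So L runs from 0 to 5.

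**Formula.** A scan on day d from randomization is d − L days after first dose. It is too early if d − L < 42. Within days 35 to 49 that gives 7 + L failing days.

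| Days too early, by lag L | 0 | 1 | 2 | 3 | 4 | 5 |
|---|---|---|---|---|---|---|
| Current rule, of 15 (days 35–49) | 7 | 8 | 9 | 10 | 11 | 12 |
| Current rule, of 8 (sites scan only on days 42–49) | 0 | 1 | 2 | 3 | 4 | 5 |
| Minimum 35 days after first dose, of 15 | 0 | 1 | 2 | 3 | 4 | 5 |
| Minimum 35 days after randomization, of 15 | 0 | 0 | 0 | 0 | 0 | 0 |

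Under the current rule, days 35–41 fail at every lag and days 47–49 pass at every lag. Days 42–46 depend on the lag. Day 42 fails whenever L is 1 or more, since 42 − 1 = 41.

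**Sensitivity.** If 6 weeks is read as study Day 42 with first dose as Day 1 (SAP 7.2.2), the failing count is 6 + L, or 6 to 11 of 15. Without a weekend in the lag, L is at most 3 and the current rule fails at most 10 of 15. A public holiday could push the count above 12.

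**Later scans.** The second scheduled scan falls on days 84 ± 7 = 77 to 91, which is 77 − 5 = 72 to 91 days after first dose. It always qualifies. An end-of-treatment scan may also qualify.

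**Scale.** In a 184-subject arm, each subject reclassified moves CBR by 1/184 = 0.54 percentage points.

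**The case against.** The strongest reply is that a minimum SD duration is legitimate and that the first-dose anchor has protocol support. Appendix C, section 5, measures SD from the start of treatment, and both documents run BOR from the start of study treatment. Any minimum will separate some subjects by scan date. All of that stands. It supports having a minimum and explains the anchor. It does not explain a threshold that a compliant first scan can miss on 7 or more of its 15 days.

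Several stronger readings are tempting, but the documents do not support them.

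- **That 7 to 12 of 15 is a share of patients.** The documents do not give the distribution of scan days or dosing lags. If sites scan only on days 42–49, the count is 0 to 5 of 8.
- **That early-only SD leaves CBR undefined.** Under Protocol 10.9.6, subjects who then progress, die, drop out or start other therapy before reaching the endpoint are non-responders.
- **That BOR has no possible place for them.** SAP 4.9.5 lists an unevaluable category. It does not say that these subjects go there, so the row is unassigned. The Appendix C entry for PD, "no prior SD, PR or CR", does not settle it, because it sits in a column headed for cases where confirmation is required.
- **That early unconfirmed CR or PR is lost too.** The 6-week sentence defines SD. SAP 4.9.4 counts CR or PR apart from SD, and SAP 4.9.5 says "Subjects with unconfirmed CR or PR assessments will be categorized separately". Whether unconfirmed responses count toward CBR is a separate question.
- **That leaving SAP 3.1 empty is a breach.** SAP 1 promises to identify only substantial differences, and Protocol 10 leaves data-handling conventions to the SAP. The size of this difference is unknown.

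**Conclusion.** The mismatch is real and minor. SD on a protocol-compliant first scan is too early to count on 7 to 12 of 15 allowed days, for dosing lags of 0 to 5 calendar days (at most one weekend, no holiday). The target day fails at any lag of 1 day or more.

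The effect is confined to subjects with SD on an early first scan and no later qualifying assessment. An arm's CBR can fall by at most the share of such subjects. The documents do not give that share, so the fall cannot be sized further. The rule is the same in all arms, so no between-arm direction or power effect follows. OS, PFS and ORR are unaffected. What remains is CBR, the last endpoint in the sequence, and the SD row of BOR.

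**What to change.** In SAP 4.9.4 and 4.9.5, replace the time condition with: at least 35 days (6 weeks minus the 7-day scan window) after randomization, computed as scan date minus randomization date. No on-schedule first scan is then too early.

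This anchor matches the scan schedule, PFS and time to response. It differs from Appendix C, section 5, and the SAP should say so. Keeping the first-dose anchor with a 35-day minimum is the closer fit to Appendix C, but it still leaves 0 to 5 of 15 days too early.

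State that SD seen only before the minimum is shown in BOR as unevaluable (early SD) and counted as no clinical benefit. Leave unconfirmed CR and PR in their existing separate category. Optionally, note the SD minimum in SAP 3.1, since Protocol 10.9.3 has none.

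The cost is one phrase in two sections and one BOR line, with no new data. The downside is a more lenient endpoint: CBR may rise slightly in all arms, and the shortest qualifying SD becomes 35 − L = 30 to 35 days from first dose instead of 42.
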